**Cancer-Related Emotional Distress and Depression.** Cancer-related distress is a significant problem for HCT and other with a negative impact on quality of life.[6, 18] Distress is far more prevalent than clinical depression, with prevalence estimated at 43% in long-term HCT survivors and moderate to severe depressive symptoms in 13-15%. [7, 19-21] Distress can be due to many factors such as uncertainty, cGVHD, managing the side effects of transplant, and financial stress.[22-24] Our preliminary research found that 41% of 2-5 year HCT survivor study participants had elevated distress on the Cancer and Treatment Distress (CTXD) measure.[25] In the cohort of 936 study participants, all but 1% of those with elevated depression scores also had elevated distress on the CTXD, suggesting that the CTXD captures a large proportion of depressive symptoms.[11] Therefore, we believe our focus on CTXD distress as the primary outcome will also address depression needs for nearly all survivors, although we will still measure depressive symptoms as a secondary endpoint. Risk factors for distress for allogeneic HCT include younger age, shorter time after HCT, and cGVHD. For autologous HCT, comorbidities are a risk factor for distress.[26, 27] Pre-HCT depression predicts later depression and other poorer outcomes[6, 27] as well as survival.[6, 28, 29] We have demonstrated that the INSPIRE online program for HCT survivors can improve distress (see 2.2 Preliminary Research). Others have demonstrated improved distress and post-traumatic stress in HCT survivors with telehealth cognitive behavioral treatment.[30]

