
#### Stratification and Randomization

Those who complete the baseline assessment but are determined to be ineligible after baseline assessment will be given access to the online INSPIRE site as a courtesy. Those who meet all eligibility criteria will be randomized based on the stratification criteria described below. If any one of the following scores on baseline patient reported outcomes (PRO) is impaired, the participant will be randomized within 'Group 1,' if no scores are impaired the participant will be randomized within 'Group 0' for the primary and secondary endpoints: a) Cancer and Treatment Distress (CTXD score <0.9 vs.  $\geq 0.9$ ), b) cardiometabolic health care adherence (<80% vs.  $\geq 80\%$ ) and c) cancer health care adherence (<80% vs.  $\geq 80\%$ ). Note that each of these endpoints of the study has a measure cut-point for eligibility for Group 1 randomization required at baseline, and these are the threestratification parameters below. However, all eligible participants will be randomized

as they will all contribute data for secondary analyses. After minimum required baseline assessment is complete and eligibility confirmed, the Project Manager will fax the registration office with stratification data for randomization. Stratification factors are based on whether the participant exceeded or fell below the cut-offs for these endpoints, as determined by baseline screening values, prior to randomization. We will not stratify on age, sex, cGVHD treatment, or race/ethnicity because we believe these will be balanced adequately between study arms through random selection, and we will adjust, or stratify on these factors as needed in analyses. Participants in both groups will then be randomly assigned to either the "Control" or "Intervention" arms. The PIs and Biostatistician will review participation rates within each stratum annually and adjust the algorithm if needed. Once enrollment is complete, the sampling probability relevant to each participant will be stored in the database for use in analyses. Randomization assignment of the participant will be communicated to the participant through email. A diagram of study randomization is shown in Figure 2 and will occur as follows.

[figure not shown]
Group 1. Meets all eligibility and has one or more elevated distress or low cardiometabolic or cancer health care adherence and is randomized to one of the two groups, intervention or control.

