## Patient Reported Outcomes (PRO)

### Primary Outcomes

*Cancer and Treatment Distress (CTXD)*. The CTXD is a 22-item inventory of distress or worry related to stressful events for cancer survivors.[25] The measure was developed by the PI from structured interviews with HCT patients, nurses and physicians and has been tested with long-term survivors (N=1978). Testing supports its value as a predictor of health outcomes and it has been used in several RCTs.[6, 148-150] Internal reliability for HCT survivors is  $\alpha = .93$ . There are 6 reliable subscales: uncertainty, health burden, family strain, finances, medical demands, identity.[151]

*Health Care Adherence (HCA)*. The HCA is derived from the Cornell Service Index.[152] We have tested the format with several thousand HCT survivors.[153] Scores are transformed to proportion of HCA recommendations met. For a primary outcome, we use HCA items reflecting adherence to cardiometabolic surveillance (HCA-cardio; 5 items). Additional items measure adherence to subsequent malignancy surveillance (HCA-cancer; 7 items) and will be a secondary endpoint (see below). Items are adjusted for sex and age at which tests are recommended. An item is scored as 'adhered to' if the participant is under the age of recommended test onset. Cut point for determining adherence for each item is based on the frequency of testing recommended in guidelines (annual, every 3 or 5 years). Score is calculated as percentage of tests completed. Since adherence is important to reduce mortality risk, we set the cutoff for not meeting adherence criteria at <80%. In our previous 6-site INSPIRE study, we found 34% not adherent to HCA-cardio surveillance using the above criteria. Validity for HCA-cardio is supported by the following associations ( $p<.01$  for all):

HCA-cardio was higher in those with self-reported high blood pressure, diabetes, history of heart attack, and those told they had cardiomyopathy or atherosclerosis. Discriminant validity is supported by no significant association of HCA-cardio with report of a history of second cancers, osteoporosis, or thyroid problems. The 21 Barriers to HCA items were defined from qualitative patient reports of HCT survivors.[154] With 6 subscales, the overall and subscale reliabilities are all  $\alpha > 0.80$ . Mean score with cut point  $>0.45$  will be used as an Aim 2 predictor. with subscales: Cost, Avoidance, Time, Knowledge, Provider Access, .

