For Hypothesis 1, the two primary endpoints, evaluated at the 12-month time point among the subjects identified at baseline as impaired for that particular endpoint criteria will each be compared between study arms as intent to treat analyses using standard logistic regression analyses, adjusted for cancer center and utilizing a two-sided  $\alpha=0.025$  level of significance to preserve type I error at 0.05 overall for the two primary endpoints. If other factors appear to be imbalanced between study arms, we will adjust analyses for those factors. Secondary analyses will evaluate depression alone, a PHQ-8 score  $\geq 10$  (essentially a subset of those with distress) and HCA-cancer in a similar manner as carried out for the primary endpoints. Continuous versions of the tests comprising the primary and secondary endpoints using linear regression models as well as adjusting or stratifying on engagement with the intervention (viewing at least 3 pages of the online program or completing telehealth calls) will also be carried out. Assumptions regarding normality of the outcomes will be assessed, although examination of outcomes in preliminary data suggests this is a reasonable assumption, with no significant skew in the distributions. If assumptions are not met, appropriate transformations will be implemented or alternative methods explored (e.g. non-parametric methods).

### Hypothesis 2

Characteristics of intervention arm participants at the 6-week interim assessment who require telehealth stepped care because they 1) do not meet criteria for adequate knowledge of subsequent malignancy and cardiometabolic risks, or 2) do not report improved distress, or 3) have not logged in to the online program will include those with higher depression or distress scores at baseline, more health care barriers at baseline, age 70+ years, male sex, people of color, lower income and education.

### Analysis Plan for Hypothesis 2

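### Beyond cancer center, covariates enter the two primary models because arms look imbalanced rather than because they were chosen in advance, which leaves the confirmatory model open and may forgo some power

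*Combined protocol and SAP*

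**What the plan says.** Section 12.7, Analysis Plan for Hypothesis 1, compares the arms at 12 months on each binary primary endpoint, among participants impaired on that endpoint at baseline, "using standard logistic regression analyses, adjusted for cancer center and utilizing a two-sided" alpha of 0.025. The stated purpose of that alpha is a "level of significance to preserve type I error at 0.05 overall for the two primary endpoints". The next sentence is the one at issue: "If other factors appear to be imbalanced between study arms, we will adjust analyses for those factors". It comes before the secondary analyses are introduced, so it governs both primary tests.

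Section 7.5, Stratification and Randomization, says: "We will not stratify on age, sex, cGVHD treatment, or race/ethnicity because we believe these will be balanced adequately" between arms, "and we will adjust, or stratify on these factors as needed in analyses".

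Neither place gives an imbalance measure, a threshold, or a statement that the choice is made without sight of outcomes. The Blinding paragraph covers site investigators and NMDP coordinators and does not mention the analyst. The three baseline cut-point flags used to stratify the randomisation (CTXD, HCA-cardio, HCA-cancer) are not named in the primary model.

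**The concern.** In a randomised trial any baseline difference between arms is a chance event. Its size says nothing about whether the factor is related to the outcome, and that relation is what makes adjustment worthwhile. The rule can bring in an irrelevant factor because it happened to differ, and leave out a strong predictor because it happened to match.

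Two things are at stake. First, without a measure or threshold, more than one model is compatible with the plan when the primary result is computed, so a reader cannot tell whether the reported p-value is the one that would have been reported anyway. Second, precision that prespecified prognostic covariates could give is mostly lost.

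**Working it through.** **1. The plan's own figures.** Table 3 (section 12.7):
- CTXD: 197 − 8 = 189; 0.75 × 189 ≈ 142, or 71 per arm.
- HCA-cardio: 239 − 10 = 229; 0.75 × 229 ≈ 172, or 86 per arm.

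For the continuous versions, power = Φ(d·√(n/2) − 2.241) at two-sided 0.025:
- d = 0.52, n = 71: Φ(3.098 − 2.241) = 0.804.
- d = 0.47, n = 86: Φ(3.082 − 2.241) = 0.800.

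Both agree with the stated 80%. For the binary endpoints the plan states a detectable relative risk of 1.9 but no control rate. Solving for 80% power gives a control rate of about 0.28 at 71 per arm (0.28 × 1.9 = 0.532) and about 0.25 at 86 per arm (0.25 × 1.9 = 0.475). These rates are assumptions from here on.

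**2. How often the rule would act.** With the four factors of section 7.5, taken as independent and fully balanced in expectation, the chance that at least one differs is 1 − 0.95⁴ = 19% at p<0.05 and 1 − 0.80⁴ = 59% at p<0.20. The plan gives no threshold, so the frequency could lie anywhere in or beyond that range.

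**3. Power without center terms.** Simulated logistic Wald tests at two-sided 0.025, 71 per arm, 0.28 vs 0.532, independent normal factors, 8,000 trials per row. The trigger is a p-value for imbalance.

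| Assumed factors | Unadjusted | Fixed list | Triggered p<0.05 / p<0.20 |
|---|---|---|---|
| one, log-OR 0.5 per SD | 0.795 | 0.822 | 0.796 / 0.801 |
| one, log-OR 1.0 per SD | 0.783 | 0.864 | 0.791 / 0.807 |
| four, log-OR 0.5 per SD each | 0.790 | 0.863 | 0.796 / 0.810 |
| four, not prognostic | 0.799 | 0.803 | 0.798 / 0.797 |

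**4. Power with center in the model, as planned.** Twelve center levels, eight candidate factors, four of them prognostic at OR 1.5 per SD:
- 71 per arm: fixed 0.836, triggered 0.791 / 0.795, a gain of 4.5 / 4.1 points.
- 86 per arm: fixed 0.831, triggered 0.793 / 0.797, a gain of 3.8 / 3.4 points.

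With only four candidates and a trigger at p<0.10, the 71-per-arm figures are 0.83 fixed and 0.78–0.79 triggered. With weak factors (OR 1.2) they are 0.80–0.81 and 0.79.

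**5. Type I error with center in the model (nominal 0.025).** In the eight-candidate setting:
- center only: 0.028–0.030
- triggered: 0.024–0.029
- fixed list: 0.030–0.033
- better of center-only and triggered at p<0.20: 0.034–0.036

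Under the alternative, those last two models disagreed on significance in 7–8% of trials.

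**6. Model size.** Intercept, arm and 11 center terms make 13 parameters. Adding a baseline value and two flags makes 16; one or two more factors make 17 or 18. At 71 per arm the assumed rates give 71 × 0.28 + 71 × 0.532 ≈ 58 successes, so 58/13 = 4.5 per parameter in the plan's own model and 58/18 = 3.2 in the largest one considered here.

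**The case against.** The best defence is that center is prespecified, that section 7.5 does name four factors, and that the plan delivers the power it promises. All of that stands. The triggered rule stays at about 0.78 to 0.81 in most of the scenarios above, so a reader who infers that the 80% claim is wrong would be mistaken. The loss is only against a better model.

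A reader might also infer that the rule makes the test conservative. Without center terms that can be seen: with four factors at log-OR 0.5, type I error is 0.0235 (p<0.05) and 0.0203 (p<0.20), against 0.0256 for the fixed list. It does not carry over to the planned model. With 12 centers and a p<0.10 trigger the rule ran at 0.027, against 0.029 for center alone.

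A third tempting step is to take the covariates straight from the protocol's background. Section 2.1 says "Risk factors for distress for allogeneic HCT include younger age, shorter time after HCT, and cGVHD", and section 8.2 says "HCA-cardio was higher in those with self-reported high blood pressure, diabetes, history of heart attack". The first concerns who has distress after allogeneic transplant (for autologous recipients the same paragraph names comorbidities). The second is a cross-sectional validity finding. Neither describes who recovers by 12 months among people already impaired at baseline, and section 8.2 does not call age or sex predictors of HCA-cardio. The documents give no prognostic strengths, so the size of any gain is an assumption.

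Finally, nothing in the documents says that a model would be picked after seeing results. That risk exists only because the wording does not rule it out. The reply to the whole defence is that none of it gives a reason to let chance imbalance decide the confirmatory model when a fixed list is available from baseline data.

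**Conclusion.** The point holds as a defect of prespecification with a modest cost in efficiency. Apart from center, the covariates of both primary models depend on observed imbalance, judged by no stated measure or threshold, and the stratification flags are not named. The power forgone is about 4 to 5 points at 71 per arm if four factors each carry an OR of 1.5 per SD, about 1 to 2 points at OR 1.2, and nothing if the factors are not prognostic. A small part of the gain with center terms reflects the slightly higher level of the larger Wald model. Mechanical use of the rule does not materially change type I error. Choosing the better of two models raises it by about 0.006 in the setting of step 5, which has eight candidates and the loosest trigger. These figures rest on control rates solved from the relative risk of 1.9, independent normal factors, equal center success rates and no missing data.

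**What to change.** Delete the imbalance sentence in section 12.7 and the conditional wording in section 7.5. Before unblinding, name one covariate list for each primary endpoint:
- cancer center, as planned;
- the continuous baseline value of that endpoint (CTXD score, or HCA-cardio percentage);
- the stratification flags that still vary in that analysis set: HCA-cardio and HCA-cancer for CTXD; CTXD and HCA-cancer for HCA-cardio;
- at most one or two further baseline factors, justified by how well they predicted 12-month outcome in the sponsor's earlier trial data.

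State that no covariate is added or dropped because of observed imbalance, and report a model adjusted for imbalanced factors only as a sensitivity analysis.

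The baseline scores and flags are already collected, so the change is one of wording. It does have a price. There are a few more parameters on 142 and 172 completers with up to 12 center levels (section 7.0 mentions 13 centers), and the Wald test already runs slightly above 0.025 there, so the list must stay short. The baseline values may also predict less than hoped, because each analysis set is restricted to impaired participants. HCA-cardio has five items, so a score below 80% can take only the values 0, 20, 40 or 60%.

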This protocol is a 12-site multicenter RCT (N=492), with Seattle as the prime site, partnering with transplant centers in Ohio, Minnesota, Wisconsin, Michigan, Massachusetts, Pennsylvania, New York, Florida, Kansas, Illinois, and Texas. This provides age, region and rural/urban diversity. Participants randomized to the intervention will receive immediate access to the tailored online program, with options for social-media, adding stepped care self-management calls for those not improving by a 6-week interim assessment for those in group 1. Control participants will receive access to a website that provides annotated links to publicly available HCT and cancer websites as well as delayed internet site access. Outcomes will be assessed at 6 weeks, 3 months and 12 months.

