## Consent

Before accessing the study questionnaires or any of the secure internet content, the electronic consent form must be agreed to and submitted. Consent will be indicated to include: 1) communication by email and phone (required), access to the secured online internet site (required), and social media (optional), 2) response to self-report assessments, and 3) allowing study access to medical records. After consenting, survivors will be registered for the study with the Fred Hutch study registration office.

Consent, with HIPAA content, will be electronically signed online. Survivors will be able to review and print the consent document before consenting via the online site, as they desire. If survivors have questions or concerns before signing the consent, we encourage them to contact us by phone or by email ([[contact]](mailto:[contact])). Consent will be obtained using forms approved by the Institutional Review Board of Fred Hutch.

*Consenting Information about Treatment Conditions.* Survivors will be told that the research focus is on decreasing distress and increasing health care understanding and actions for people 2 to 5 years after transplant. They will be told that there are two possible groups: 1) full INSPIRE online program and study materials access, with mailed treatment summary and survivorship care plan (TS-SCP) for the survivor and, if they choose to provide names, for their health care providers, with an optional orientation call at 2 weeks and optional self-management calls at 6 weeks; or 2) access to a study website with links to other online resources for survivors, with delayed INSPIRE program access after completion of the 12-month assessment. They will be advised that they will be contacted if we detect severe emotional needs during the course of the study.

The first 100 participants who are approached, with an expected N=20 enrolled for the randomized study, will be treated as "run in" participants to test the website programming and study intervention procedures.

They will be approached and treated as regular participants from survey to data management randomization and intervention. These participants will receive the same access and study experience as later participants, but they will not be included in the outcome analyses or the N=492 sample size. Thus the total enrollment is projected to be N=512.

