*Stepped Care Self-Management Telehealth Contacts.* Group 1 intervention participants who at the T2 (6 weeks) indicate no use of the online program, or lack knowledge of their cardiometabolic or subsequent malignancy risks, or do not indicate improvement in distress, will receive telehealth contacts. These will be three to four calls via phone. Calls will last 20-30 minutes for the first call and 10-20 minutes for the 'booster' calls. They will be led by a 'coach' trained by the clinical investigators in HCT and self-management skills, using a manual to deliver call content focused on assisting survivors with using the self-management skills in the online program. This is a brief, manualized intervention is designed to be sustainable without extensive clinical training and has been tested. The first session will focus on impairments indicated by the T2 6-week screening PRO. The coach and participant will make shared decisions, led by the participant, on goals and an action plan for addressing deficits, and elicit potential barriers and their solutions based on chronic disease self-management models (Figure 1).[1, 84, 133, 140-143] The second and third 'booster' calls will review progress on the action plan, address barriers and agree on a revised plan if needed. Participants and coaches will decide whether a fourth call would be helpful based on the complexity and difficulty of the goals and action plans. The contacts will be audiotaped for process evaluation

of content and fidelity to the self-management script.

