## 8.0 EVALUATION

Table 1. PRO Measures and schedule of administration (T2 for intervention-only participants described in section 8.1)

8.1 Patient Reported Outcome Measures	T1 Baseline Screening	T3 3 month Outcome	T4 12 month Outcome
Primary Outcomes			
Cancer and Treatment Distress (CTXD)	X	X	X
Health Care Adherence (HCA)	X		X
Secondary Outcomes			
Patient Health Questionnaire-8 Depression (PHQ8)	X	X	X
Moderators and Risk Factors			
Computer and Mobile Phone Use	X		
Background: potential barriers to PCA (age, income, rural/urban, gender, cancer and treatment history, current medical history, medications)	X		
GVHD Symptom Scale (allogeneic only)	X		
Medical Comorbidities and Medications	X		X
Mediators			
Knowledge of Survivorship Needs	X	X	X
Health Self-Efficacy	X	X	X
Study Evaluation			
Evaluation of Program and Participation			X
ESTIMATED TIME REQUIRED	30-40	10-15	25-35

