## Measurement Time Points

The measures and their administration time points for three of the four assessments are listed in Table 1: baseline, 3 and 12 months. For group 1 intervention participants only, there will also be a brief orientation call for the study at 2 weeks, and an assessment at 6 weeks, that determines distress and knowledge of survivor health risks. Distress is measured on a 0-10 distress thermometer rating scale (0=no distress, 10=extreme distress) is >5, along with the first 2 items on the PHQ scored <=2 indicating low distress and depression symptoms. The distress thermometer is a widely used, validated and reliable measure of distress in cancer survivors.[144-147] Knowledge of HCT Survivor Health Risks is an 11-item screening for cardiometabolic and subsequent malignancy risks. Items are scored 0 ('my risk is higher') or 1 ('my risk is not different' or 'not sure') with a score >2 indicating inadequate knowledge of risks and eligibility for telehealth stepped care. The third criterion is whether the participant has viewed at least 3 pages of the online INSPIRE site. If any one of these 3 progress criteria are not met, intervention participants are stepped into telehealth self-management contact as described in Treatment section 7.5.1.

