## Study-Specific Adverse Event Capture and Data Safety and Monitoring Plan

Based on previous similar research with internet-based behavioral treatment conducted with survivors who have recovered from acute treatment effects and are living independently, this study is not expected to have Serious Adverse Events (SAE). We will contact and collect data from participants at baseline, 6-weeks, 3 months and 12 months. We plan ongoing recording of adverse events for each participant, each reviewed by the PI within 7 days. Any SAE will be immediately reported to the PI and the IRB according to requirements in the standard Fred Hutch DSMP. As Coordinating Center, Fred Hutch will complete the Fred Hutch/UW Cancer Consortium Expedited Reporting Form for all adverse events, including those associated with participants enrolled from the participating consortium centers. Ad hoc meetings will be called by the PI for any SAE, for two similar Adverse Events, or at any time by any other study staff or investigator for a data or participant safety concern. A physician member of the research project will provide the medical monitoring for all adverse events. Adverse events and SAE will be reviewed annually by the Fred Hutch standing Data Safety and Monitoring Board and Institutional Review Board in addition to the immediate reviews for SAE just described.

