Among subjects in Group 0 and Group 1 intervention arms, we will define the endpoint as a binary indicator of whether the individual required telehealth stepped care at the 6-week time point. We plan to use generalized linear models to evaluate associations between patient characteristic variables and likelihood of stepped care. Variables to be examined include age (<70 vs. 70+ years), sex, race/ethnicity (White non-Hispanic vs. Non-White or Hispanic), income ( $<\$40,000$  vs.  $\$40,000$  per year) and education (college graduate yes/no), PHQ8 depression  $>16$ , and Barriers to HCA  $> 0.45$ . The need for telehealth stepped care is not likely to be a rare event (rare being  $<10\%$ ) and thus odds ratios from a logistic regression model would not be good approximations of the relative risk (RR). Therefore, rather

	CTXD	HCA-Cardio	
Enroll/Consent/complete baseline	492	492	
T1: Eligible for specific endpoint	197	239	
3 mo. voluntary withdraw or mortality/illness (4%)	[8]	[10]	
3 mo. non-responders, able to respond at 12 mo. (15%)	[30 eligible for T4]	[36 eligible for T4]	
T3: 3 mo. completers (81%)	160	194	
T4: 12 mo. potential cohort	189	229	
12 mo. voluntary withdraw or mortality/illness (5% of T4)	[9]	[11]	
12 mo. non-responders (20% of T4)	[38]	[46]	
12 mo. completers (75% of T4, 72% of T1)	142	172	
	[71/arm]	[86/arm]	

than logistic regression we will likely use a log-link with Poisson error structure and robust sandwich variance estimates to directly estimate the more interpretable RR.[173] A multivariable model will be established using single-variable and step-up and step-down procedures with a liberal p-value for inclusion in the model ( $p<0.2$ ). Factors identified as significantly ( $p<0.05$ ) associated with the need for telehealth stepped care will be examined and based on the magnitude of the RR estimate and the prevalence of the particular patient characteristic, we will similarly examine indicators of response to the telehealth care based on continuous primary endpoints in that subgroup. This will establish a profile of types of survivors for whom modified approaches to care may be beneficial.

### Aim 3 and Plan for Aim 3

Determine resources that would be needed to sustain the intervention as a national HCT survivorship program if implemented through the CIBMTR/NMDP.

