This is a descriptive aim defining costs and resource requirements. Data relevant to resource utilization (costs) and methods of collection are described in section 8.3 Cost and Resource Tracking. All costs associated with the intervention and, separately, the control arms of the study for the Group 0 and Group 1 subjects in the study will be summed and standardized to per person costs. We will use these amounts to calculate an incremental cost ratio for the online intervention program and telehealth intervention component compared to the control cost, similar to the method described by Mandelblatt et al.[171, 172] The costs of maintaining the various components of the program, relative to their use, will be calculated separately for those in the Group 0 and 1 intervention arms, specific to maintaining the social media site, the internet program, and the telehealth calls (Group 1 only) relative to the number of participants using those components among intervention participants.

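### The Aim 2 analysis includes the Group 0 intervention arm, for which the stepped-care endpoint is not defined, and its predictor list omits baseline distress

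*Combined protocol and SAP*

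**What the plan says.** The Analysis Plan for Hypothesis 2 (section 12.7) begins its definition of the population and of the 6-week endpoint, need for telehealth calls: "Among subjects in Group 0 and Group 1 intervention arms, we will define the endpoint as a binary indicator of whether the individual required". Relative risks are to be estimated by Poisson regression with robust variance. The listed predictors are age, sex, race/ethnicity, income, education, PHQ-8 above 16 and Barriers to HCA above 0.45.

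Four places limit the assessment or the calls to Group 1:
- Section 8.1, Measurement Time Points, on the 6-week assessment: "For group 1 intervention participants only, there will also be a brief orientation call for the study at 2 weeks, and an assessment".
- Section 1.0: "adding stepped care self-management calls for those not improving by a 6-week interim assessment for those in group 1".
- Section 7.6 opens its rule for the calls with "Group 1 intervention participants who at the T2 (6 weeks) indicate no use of the online program".
- The Aim 3 plan in section 12.7 costs "the telehealth calls (Group 1 only", closing the parenthesis there.

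Other text is looser. The title of Table 1 (section 8.0) has "T2 for intervention-only participants described in section 8.1". Section 10.2 says "We will contact and collect data from participants at baseline, 6-weeks, 3 months and 12 months". Section 7.3 describes the intervention group "with an optional orientation call at 2 weeks and optional self-management calls at 6 weeks". Section 1.0 lists 6 weeks among the outcome times, and the closing sentence of Measurement Time Points speaks of intervention participants in general. None of these names Group 0 or gives a coding rule for it.

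Hypothesis 2, in sections 12.6 and 12.7, names higher baseline depression or distress as an expected characteristic.

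**The concern.** Stepped care is triggered by failing any one of three criteria: 6-week distress, 6-week knowledge of risks, and use of the site. The first two come from an assessment that Group 0 does not receive. Site use could be read from the logs described in section 8.3. But a Group 0 participant who meets that criterion cannot be classified on the other two, and one who fails it is still not stepped up under section 7.6.

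The literal result of applying a Group 1 rule to Group 0 is to code all of Group 0 as *not required*. Those participants are then structural zeros. Any predictor concentrated in Group 1 will appear to predict need because of the eligibility rule. Depression is the clearest case. Section 2.1 reports that about 99% of survivors with elevated depression also had elevated CTXD, and elevated CTXD places a participant in Group 1 (section 7.5).

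The plan uses predictors with p<0.05, and the size of their relative risks, to profile survivors who may benefit from modified care. An artefact of eligibility could enter that profile as patient need. Section 3.1 lists Aim 2 as a primary aim, although section 12.6 places it under secondary hypotheses.

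**Working it through.** The plan gives no sample size, power or relative risk for Aim 2, so there is no stated figure to reproduce.

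**Group sizes.** With 492 randomised and 1:1 allocation assumed, 246 are in the intervention arms. Three values are used for Group 1 (both arms):
- 305, from section 12.2, where the figure is tied to the two primary endpoints.
- 387 = 492 × (1 − 0.59 × 0.66 × 0.55). This uses 41% elevated distress (section 2.1), and 34% low HCA-cardio and 45% low HCA-cancer (section 8.2), assumed independent.
- 409 = 492 × (1 − 295/492 × 253/492 × 0.55). This replaces 41% and 34% with Table 3's 197 and 239 of 492.

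The Group 0 share is 187/492 = 38.0%, 105/492 = 21.3% or 83/492 = 16.9%.

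**Null relative risk with Group 0 coded *not required*.** Let N1 and N0 be the group sizes, and let f = prevalence × 492/N1 be the share of Group 1 with the predictor. Suppose the predictor occurs only in Group 1 and need is unrelated to it there, at rate p. Need is p in those with the predictor and p × N1(1−f)/[N1(1−f)+N0] in the rest, so

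RR = 1 + N0/[N1(1−f)].

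Example: N1 = 305 and prevalence 5% give f = 24.6/305 = 0.081 and RR = 1 + 187/280.4 = 1.67.

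The documents give no prevalence for PHQ-8 above 16. It should lie between the severe category (below 1% in section 7.4, 2% expected in section 12.3) and the broader 13–15% with moderate to severe symptoms in section 2.1.

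| Assumed prevalence | N1=305 | N1=387 | N1=409 |
|---|---|---|---|
| 1% | 1.62 | 1.28 | 1.21 |
| 2% | 1.63 | 1.28 | 1.21 |
| 5% | 1.67 | 1.29 | 1.22 |
| 14% (upper bound) | 1.79 | 1.33 | 1.24 |

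These values place all depressed participants in Group 1. Using 99% instead lowers them by about 0.01–0.02.

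**False-positive rate.** For each setting, 40,000 trials of 246 were simulated with need unrelated to the predictor within Group 1. The test was a two-sided 0.05 Wald test of the log relative risk with a single predictor. Trials with an empty event cell counted as not significant. The plan says only that need will not be rare, so rates of 30, 50 and 70% are assumed. Ranges run over the three Group 1 sizes.

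| Prevalence | Group 0 coded *not required* (need 30 / 50 / 70%) | Group 1 only |
|---|---|---|
| 1% | 16–18 / 24–29 / 40–45% | 12–13 / 22 / 39% |
| 2% | 13–20 / 19–30 / 29–47% | 8–9 / 12–13 / 22–23% |
| 5% | 11–27 / 17–43 / 27–65% | 5 / 6–7 / 9% |
| 14% | 15–49 / 25–76 / 43–95% | 5 / 5 / 5–6% |

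The coding adds about 1–8 points at 1% prevalence and about 5–24 points at 2%. The Group 1 rates above 5% reflect very small counts: 2% of 246 is about 5 people.

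**Predictor list.** Set against Hypothesis 2, every named characteristic has a variable except baseline distress. CTXD is collected at baseline (Table 1, section 8.0).

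**The case against.** The inflation depends on a coding that no section states. If Group 0 is treated as missing, the analysis reduces to Group 1 and the bias is nil. That is correct and limits the claim about harm, but section 12.7 would still describe a population other than the one analysed.

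A milder coding is possible, because failing the site-use criterion alone suffices under section 8.1. Suppose Group 0 is scored on site use alone, with 23% non-use (section 2.2: 77% of the first study's intervention participants logged in). The null relative risk is then 1.04–1.42 for need of 30–70%. The bias is smaller but still upward.

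The largest figures rest on Group 1 = 305, while low HCA-cancer also admits participants to Group 1. At 387–409 the null relative risk is 1.21–1.33, and at 1–2% prevalence the coding adds only about 1–9 points to the false-positive rate. The 14% row describes a broader category than PHQ-8 above 16 and is only a ceiling. At 1–2% prevalence, sparse data are often the larger problem, and restricting the population does not cure that.

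The predictor list is introduced as a list of inclusions and may not be closed, so the distress point is a gap in specification rather than a demonstrated error. Aim 2 is also exploratory in method, with stepwise selection and no stated power. These points limit the size of the problem. They do not remove the contradiction.

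**Conclusion.** The concern holds and should be fixed. The contradiction over Group 0 and the missing distress variable are certain from the text. The bias is conditional on Group 0 being coded *not required*. Its direction is then upward throughout, with a null relative risk for depression of about 1.2–1.7 at 1–5% prevalence and at most 1.79 at the 14% ceiling.

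These sizes assume 1:1 allocation, the stated range for Group 1, an assumed prevalence and need rate, a single-predictor model (the plan's is multivariable), and that PHQ-8 above 16 overlaps with elevated CTXD as elevated depression does in section 2.1.

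No artefact is claimed for age, sex, race/ethnicity, income or education. Barriers to HCA may be affected, but the documents give no overlap figure. The harm is confined to which factors enter the Aim 2 profile and how large their relative risks look. The later step, response to telehealth, concerns people who received calls.

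**What to change.** 1. Restrict the Hypothesis 2 analysis to the Group 1 intervention arm, the only arm for which the plan defines the assessment and calls. Reconcile section 12.7 and the looser wording in sections 1.0, 7.3, 8.0, 8.1 and 10.2 with that. If Group 0 is meant to be included, state how it is assessed and coded, and report the two groups separately.
2. Add baseline CTXD to the predictor list, with its form or cut-point. Do this together with step 1: CTXD of 0.9 or more itself places a participant in Group 1, so the same artefact would arise if Group 0 stayed in as zeros. Within Group 1, everyone below 0.9 has low adherence by definition, and the CTXD estimate should be read with that in mind.
3. Reconcile the site-use criterion used in the endpoint. Section 7.6 refers to no use, section 8.1 to viewing three pages, and Hypothesis 2 to not having logged in.
4. State how a missing 6-week questionnaire is handled, by a method that does not select on the outcome, for example multiple imputation with a sensitivity analysis. Section 12.7 plans this for the primary outcome only.

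The cost is a wording change and an imputation step of a kind already planned. Steps 1 to 4 need no new data, although assessing Group 0 instead could. The nominal sample falls from 246 to about 152–204 (half of 305 to 409), but those removed have no defined endpoint. With about 5 participants above the PHQ-8 cut-off at 2% prevalence, the Wald test for that predictor remains unreliable even in Group 1 alone, and the report should say so.
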